3 STUDY DESIGN

3.1 Overview of Study Design

This will be a double-blinded, placebo controlled randomized clinical trial to evaluate the efficacy of NCG in the treatment of two organic acidemias (severe PA and MMA), and two urea-cycle disorders (late-onset CPSD and OTCD). Figure 3 summarizes the design of the proposed trial.

Figure 3. Study Overview Diagram

Protocol Overview

- Eligibility** – Briefly, subjects (a) aged >1 week with verified diagnosis of CPSD or OTCD or (b) subjects of any age with verified diagnosis of PA or MMA and ammonia level \geq 70mcmol/L. All subjects (or a first-degree relative) must have had a recorded plasma ammonia \geq 100 mcmol/L and must have presented initially at >1 week of age for CPSD or OTCD. Subjects must not be pregnant. A complete listing of eligibility criteria is included in Section 4 (Study Population).
- Enrollment** – Informed consent from the participant or one parent or legal guardian.
- Randomization** – At each hyperammonemic episode, participants will be randomized to either placebo plus standard therapy (PLBO-STD) or NCG plus standard therapy (NCG-STD) at a dose of 150 mg/kg/ day or 3.3 g/m²/day for patients >15 kg, divided into 2 equal doses and administered enterally by nasogastric or gastrostomy tube or by oral syringe.
- Study Treatment** – The NCG/PLBO dose will be administered for metabolic decompensation for 7 days or until discharge, whichever is shorter.
- Concomitant Standard Treatment** – Participants will continue receiving standard treatment which may include intravenous glucose (and insulin if required), L-carnitine dosing and/or dialysis. Ammonia scavengers may only be administered in patients with urea cycle disorders.

- **Laboratory Measurements** – Plasma ammonia testing should be performed as clinically indicated, including checking the level at admission and at least every 6-12 hours for the first 48 hours and every day thereafter if the previous level was ≥ 50 $\mu\text{mol/L}$, for a total of 7 days or until discharge, whichever is shorter. Plasma amino acids should also be checked as clinically indicated at admission and at least every 2 days thereafter, if ammonia levels are measured. Safety laboratory assessments including complete blood cell count, liver and kidney function tests, amylase and lipase testing, as well as a coagulation profile (if clinically indicated) will be done at the time of initial admission, at 3-5 days, at 6-7 days or at discharge, whichever is shorter.

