^a Suggested timeline to be followed for 7 days, or until discharge if discharged prior to 7 days of drug administration

^b For women of childbearing potential only. A serum pregnancy test will be performed in the event of a positive or equivocal urine pregnancy test result, or if the patient is anuric

^c Allowable windows for day 3 (days 3-5) and day 7 (days 6-7), unless otherwise indicated

^d Plasma ammonia should be drawn as frequently as clinically indicated, for example, every 6 hours during the first 24-hour window if the patient has a central or peripheral venous catheter.

^e Only to be drawn if dialysis is performed. Blood draws should be performed immediately upon termination of hemodialysis or hemofiltration, even if the regular time-point labs have been drawn.

^f Plasma ammonia should be drawn as frequently as clinically indicated, for example, after 48 hours, follow-up ammonia should be obtained if the prior measurement was ≥ 50 μ mol/L

^g Amino acids should be drawn as frequently as clinically indicated, for example, obtained only if ammonia also obtained (see f)

^h Safety Lab blood draw to be obtained on day 6-7, or if discharged <7d, within 24h prior to discharge

ⁱ EKG should be done before treatment begins and repeated once between Days 3-5 or before discharge

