5.4.1.3 Post-Randomization

Day 1

Short-Term Outcome of NCG in Hyperammonemia

1. As per their assignment, the participant will be started on NCG (150 mg/kg/day for patients ≤15 kg or 3.3 g/m²/day for patients >15 kg in two divided doses) OR PLBO (three-quarters tablet/kg/d for patients ≤15 kg or 16.5 tablets/m²/day for patients >15 kg, in two divided doses) to be administered through a nasogastric tube, or if not available, by oral syringe, as described in Section 6.1. The participant will also continue to receive standard therapy.
2. Following the first drug administration, the subsequent drug administration should be given between 6 and 12 hours after the first dose, at a standard drug administration time for the site. All subsequent doses should be given every 12 hours.
3. Indicated clinically, plasma ammonia testing will be performed every 6 hours following study drug administration if the patient has a central or peripheral catheter. In all other cases, plasma ammonia testing will be performed every 12 hours, as indicated clinically.
4. Clinical monitoring FSS
5. Treatment administration log, concomitant medications log, blood transfusion log, and adverse events log will be completed daily

Day 2

1. NCG/PLBO Rx. & Standard Rx every 12 hours.
2. Plasma ammonia every 12 hours (as indicated clinically)
3. Amino acids (as indicated clinically)
4. Clinical monitoring FSS
5. Treatment administration log, concomitant medications log, blood transfusion log, and adverse events log will be completed daily

Day 3 (if not yet discharged)

1. NCG/PLBO Rx. & Standard Rx every 12 hours.
2. Plasma ammonia (as indicated clinically)
3. Safety labs should be performed between days 3 - 5
4. EKG test should be performed between days 3-5
5. Clinical monitoring FSS
6. Treatment administration log, concomitant medications log, blood transfusion log, and adverse events log will be completed daily

Day 4 (if not yet discharged)

1. NCG/PLBO Rx. & Standard Rx every 12 hours.
2. Plasma ammonia (as indicated clinically)
3. Amino acids (as indicated clinically)
4. Clinical monitoring FSS
5. Treatment administration log, concomitant medications log, blood transfusion log, and adverse events log will be completed daily

Day 5 (if not yet discharged)

1. NCG/PLBO Rx. & Standard Rx every 12 hours.
2. Plasma ammonia (as indicated clinically)
3. Clinical monitoring FSS

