5.5 Study Assessments

5.5.1 Laboratory Tests

- Plasma ammonia (as indicated clinically)
- Plasma amino acids (as indicated clinically)
- Complete blood cell count
 - White blood cells and differential
 - Platelets
 - Hemoglobin
 - Hematocrit
- Liver function tests
 - ALT (Alanine Aminotransferase)
 - AST (Aspartate Aminotransferase)
 - Alkaline phosphatase
 - Direct bilirubin
 - Total bilirubin
 - Albumin
 - Total protein

Short-Term Outcome of NCG in Hyperammonemia

- Kidney function tests
 - Blood urea nitrogen
 - Creatinine
- Amylase and lipase
 - Amylase
 - Lipase
- Coagulation profile (as indicated clinically)
 - PTT (Partial Thromboplastin Time)
 - INR (International Normalized Ratio)
- Pregnancy test (if applicable)

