We propose to use Cox Proportional Hazard modeling to implement the primary analysis to compare the average differences in time to reach the composite outcome and allow us to control for differences in severity (ammonia level and or FSS) at episode baseline. This method will also allow us to take account of and adjust statistical testing for the correlation between results of participants who contributed more than one event to the analysis. The comparison of slopes of the ammonia decline curves by treatment group will shift to secondary analysis, which will allow us to focus on consistency of results rather than choosing the precise model for significance testing for the purpose of rejecting the null hypothesis of no treatment effect.

Study analyses will be based on an intention-to-treat paradigm. In analyzing the primary outcome, we will evaluate the difference over time in the probability of reaching an ammonia level of 50 $\mu\text{mol/L}$ or hospital discharge. For this purpose, we will use a z-test to assess the evidence that the hazard (event) ratio (HR) differs from 1 (no effect) to test for a difference in the probability of the composite outcome over time by the group. We will account for the correlation between repeat episodes per participant by treating participant episodes with the same ID as a cluster, which will adjust standard error estimates for the intraclass correlation between episodes in the same cluster. The primary analysis will be implemented using the sts cox procedure in Stata 14 (StataCorp. *Stata Statistical Software: Release 14*, College Station, TX: StataCorp LP, 2015).

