8.4 Rationale for Sample Size and Statistical Power

All sample size and power estimates are based on 2-tailed testing, which assumes a type 1 error of 5% and achieving 80% power to detect an HR difference by treatment group and that there is no censoring as each episode will contribute information to one of the composite outcomes. We used the Cox Regression procedure in PASS (Hintze, J. PASS 11. NCSS, LLC. Kaysville, Utah, USA. www.ncss.com, 2011) to evaluate the composite time to event outcome of the earlier of the time to reach an ammonia level of 50 μ mol/L or time to discharge within hyperammonemic episodes (the unit of randomization and analysis). We evaluated HR estimates above 1, reflecting that the NCG group achieved the higher probability of achieving the composite event. Based on these considerations, a total sample size of N=146 episodes can detect an HR of 1.6, one of N=114 can detect an HR of 1.7, one of N=93 can detect an HR of 1.8 and one of N=78 can detect an HR of 1.9. These sample size estimates account for an inflated R-square as large as 0.05 between the time to event outcome and covariates reflecting baseline severity at the start of an episode. We used the inflated R-square to account for the modest effect of clustering of episodes within a person. Therefore, we consider the originally-targeted sample size of 144 episodes to be more than sufficient to meet the aims of the study. Based on our re-analysis of the time-to-event outcome, an HR of 1.7 is realistic and a sample size of 114 episodes is sufficient to detect that effect. Therefore, the target sample size will be 114 episodes.

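### Ammonia draws set the primary event time, but the sections disagree on whether a minimum draw interval binds, and section 8.3 names no method for the ties that scheduled draws create

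*Combined protocol and SAP*

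**What the plan says.** The synopsis and section 8.3 define the primary outcome as the earlier of reaching the ammonia target of 50 µmol/L and hospital discharge. The sections then word the ammonia draws differently:

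- **Section 3.1 (Laboratory Measurements)** opens with clinical indication but adds a floor: "at least every 6-12 hours for the first 48 hours and every day thereafter if the previous level was" at or above 50 µmol/L, up to 7 days or discharge.
- **Section 5.4.1.3** ties Day 1 draws to vascular access: 6-hourly with a catheter, otherwise "In all other cases, plasma ammonia testing will be performed every 12 hours, as indicated clinically". Day 2 is 12-hourly, again subject to clinical indication. From Day 3 on, clinical indication is the only rule.
- **Table 1 (section 5.4.1.2)** prints draws at 0, 6, 12, 18, 24, 36 and 48 h and daily afterwards, but its footnote calls this a "Suggested timeline to be followed for 7 days, or until discharge if discharged prior to 7 days of drug administration". Footnotes d and f offer the intervals as examples only.
- **Section 5.5.1** lists "Plasma ammonia (as indicated clinically" with no interval.

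On analysis, section 8.3 says "The primary analysis will be implemented using the sts cox procedure in Stata 14", with episodes clustered by participant so that standard errors are adjusted. It names no method for tied times and does not mention the interval between draws. Section 8.4 assumes that "there is no censoring as each episode will contribute information to one of the composite outcomes".

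**The concern.** There are two linked problems.

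**Ascertainment.** A site that skips a Day 3 redraw in an unresolved episode complies with section 5.4.1.3 and breaches the floor in section 3.1. If no value below 50 µmol/L is recorded, the composite times that episode at discharge. Section 8.3 itself says that the complications that keep a patient in hospital after ammonia resolves are not expected to respond to the drug. Time added this way would carry little treatment signal and could pull the HR toward 1. The same clinical course could therefore get a different event time, and a different event component, depending on which section a site follows.

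**Ties.** Even with every draw made, resolution is seen only at draw times, so many episodes share an event time. The Cox estimate then depends on the tie method. One common approximation (Breslow) shrinks the HR when ties are heavy. The reported HR is the trial's effect estimate, so the method should be fixed in advance.

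**Working it through.** **1. The plan's own figure.** Section 8.4 specifies "2-tailed testing, which assumes a type 1 error of 5% and achieving 80% power to detect an HR difference by treatment group", and states that "one of N=114 can detect an HR of 1.7". By Schoenfeld's formula with 1:1 allocation:

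- Events = 4 × (1.960 + 0.842)² / (ln 1.7)² = 111.5, so 112.
- Power with 114 events: √114 / 2 × 0.5306 − 1.960 = 0.873, which gives 80.9%.
- With the stated R-square of 0.05, power at 114 is 78.9%.

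The plan's figure is reproduced. It treats event times as exactly observed.

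**2. Assumptions for the sampling check.** The documents give no resolution times, discharge lags or share of undrawn episodes, so all of these are assumed:

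- 57 episodes per arm, treated as independent, with true HR 1.7.
- Time T to ammonia below 50 µmol/L is exponential, with control median 18-36 h.
- Discharge D = T + 12 h + an exponential lag of mean 24-60 h, the same in both arms.
- Observed time = the earlier of D and T rounded up to the next draw. For an episode not redrawn, observed time = D.
- Draw grids: Table 1, or 12-hourly to 48 h and then daily.

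**3. Effect of missing redraws (Efron ties).** Redraws are stopped from 48 h, because section 5.4.1.3 still prints 12-hourly draws on Day 2.

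| Setting | Estimated HR | Power |
|---|---|---|
| Schedule kept | 1.66-1.72 | 74-81% |
| Half of episodes unresolved at 48 h not redrawn | 1.61-1.70 | 68-78% |

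Half of those unresolved at 48 h is about 5-15% of all episodes. The loss is clearest with the long lag (60 h) and medians of 24-36 h. Elsewhere it is close to simulation error.

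The discharge model matters. If discharge falls at twice the resolution time, leaving episodes undrawn makes no material difference (Table 1 grid, Breslow ties): HR 1.57-1.60 with none undrawn, 1.60 with 20% undrawn and 1.62-1.64 with 50% undrawn.

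**4. Effect of the tie method, schedule fully kept.** At a single tied draw time, the Breslow estimate equals the ratio of the two arms' proportions resolving in that interval. For a control median of 24 h and true HR 1.7:

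- 6 h interval: (1 − 2^−0.425) / (1 − 2^−0.25) = 0.255 / 0.159 = 1.60.
- 12 h interval: (1 − 2^−0.85) / (1 − 2^−0.5) = 0.445 / 0.293 = 1.52.
- 24 h interval: (1 − 2^−1.7) / (1 − 2^−1) = 0.692 / 0.500 = 1.38.

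The full simulation agrees:

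| Tie method | Draw grid | Estimated HR |
|---|---|---|
| Breslow | Table 1 | 1.53-1.60 |
| Breslow | 12-hourly | 1.46-1.58 |
| Efron | either | 1.66-1.72 |

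**5. Power under Breslow.** With robust standard errors, as section 8.3 plans, power stays at about 76-80%. With model-based standard errors the same approximation shows roughly 50-73% across the settings tried, because those errors are too wide when ties are heavy. The planned analysis is the robust one, so the harm is to the estimate.

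**The case against.** The strongest case on the other side is that the sections are closer than they first appear. Section 3.1 also mentions clinical indication. Section 5.4.1.3 prints intervals for Days 1 and 2. The Table 1 grid matches section 3.1, and footnote f asks for a follow-up draw when the previous value was 50 µmol/L or more. Section 8.3 treats the target level as the point where discharge becomes possible, so a patient still above it has a clinical reason to be redrawn. Nothing in the documents says that sites stop testing. All of this stands, and it confines the real gap mainly to Day 3 onward. It does not remove the gap: only section 3.1 and the Table 1 example footnote cover those days, and the operational section does not.

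A reader might infer that the HR and power will fall. The documents do not support that as a fact. It depends on how many episodes go undrawn and how closely discharge follows resolution, and neither is given.

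A reader might also quote power of 60-76%, which comes from stopping redraws at 24 h. That does not measure the Day 3 gap, because 12-hourly draws are still printed for Day 2.

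It is also fair to say that the tie problem is not caused by the wording conflict. It exists with perfect sampling and should be judged separately. Its size depends on the grid, and the lowest HR values belong to the sparser 12-hourly grid.

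**Conclusion.** The wording conflict is real and bears on the primary endpoint. Its effect can be a diluted HR, but the documents fix neither its size nor its direction. In the 48 h scenario the estimate moves from 1.66-1.72 to 1.61-1.70 and power from 74-81% to 68-78%. There is little or no loss where discharge closely follows resolution.

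The missing tie method is the firmer of the two points. With a true HR of 1.7 and every draw made, a Breslow approximation would report about 1.53-1.60 on the Table 1 grid or 1.46-1.58 on a 12-hourly grid, where Efron stays near the truth. The plan does not say which method will be used, so this is a risk and not a known bias. A reader might conclude that Breslow ties would also cost the trial its power. Under the cluster-robust errors planned in section 8.3 they would not.

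These ranges rest on exponential resolution times, a discharge lag unaffected by treatment, and no correlation between episodes of one participant.

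**What to change.** 1. **Section 8.3:** specify Efron or exact handling of ties for the primary Cox model. State that it also applies to the interim analysis in section 8.3.1. This costs one model option.
2. **Sections 3.1, 5.4.1.2 (Table 1 and its footnotes), 5.4.1.3 and 5.5.1:** reconcile these so that one identically worded ammonia schedule governs endpoint ascertainment until the first value below 50 µmol/L, discharge or the end of the sampling period. The interval, and how far clinical discretion applies, are for the sponsor to decide. The cost is protocol wording. If the agreed schedule is binding, some draws now left to discretion would become required, which the sponsor should weigh because the trial includes neonates.
3. **Optional:** add a sensitivity analysis that places resolution between the last value at or above 50 µmol/L and the first value below it, using an interval-censored or grouped-time proportional hazards model. It needs only the draw times and values the trial already records.

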5.4.1.4 Discharge Procedures

If still on NCG/PLBO, the subjects will be discontinued from the study drug at the time of discharge from the hospital.

We will contact subjects or their families to collect any adverse events that occurred in the 72 hours following episode treatment completion.

5.5 Study Assessments

5.5.1 Laboratory Tests

- Plasma ammonia (as indicated clinically)
- Plasma amino acids (as indicated clinically)
- Complete blood cell count
 - White blood cells and differential
 - Platelets
 - Hemoglobin
 - Hematocrit
- Liver function tests
 - ALT (Alanine Aminotransferase)
 - AST (Aspartate Aminotransferase)
 - Alkaline phosphatase
 - Direct bilirubin
 - Total bilirubin
 - Albumin
 - Total protein

Short-Term Outcome of NCG in Hyperammonemia

- Kidney function tests
 - Blood urea nitrogen
 - Creatinine
- Amylase and lipase
 - Amylase
 - Lipase
- Coagulation profile (as indicated clinically)
 - PTT (Partial Thromboplastin Time)
 - INR (International Normalized Ratio)
- Pregnancy test (if applicable)

5.5.2 Electrocardiogram test (EKG)

QT interval and QTc interval will be collected from each EKG, along with any abnormalities noted in the interpretation

5.5.3 Transfusion Information

Type of transfusion (e.g., packed red blood cells, fresh frozen plasma) and number of units will be collected

5.5.4 Clinical Assessments

The secondary objective of this study is to evaluate the impact of NCG treatment on the functional status scale. During each admission, the functional status scale will be evaluated prior to the start of study drug, as well as every day thereafter, until discharge or until episode treatment completion of the study drug.

5.5.4.1 Pharmacokinetic Assessments (CNMC & CHOP)

**** THIS PROTOCOL SECTION ONLY PERTAINS TO CHILDREN'S NATIONAL HOSPITAL AND CHILDREN'S HOSPITAL OF PHILADELPHIA (CHOP) ****

Left over plasma or serum from any sample drawn for clinical laboratory tests will be saved for pharmacokinetic (PK) analysis to be paired with study drug dosage and time of administration. The plasma and/or serum samples will be stored frozen at -20°C and batch-shipped on dry-ice to Atlanbio Laboratory ([name]) for determination of N-carbamylglutamate levels at the end of each patient episode. Since study participants experience a high number of blood draws for clinical tests, no additional blood will be drawn specifically for PK analysis. There will be no schedule of assessments for PK samples. Instead, study staff at CNMC and CHOP sites will be encouraged to collect the left over plasma or serum samples during each hyperammonemia episode. The exact time and date of the blood draw is recorded (and will correspond to the medical record) for each sample. These samples will be stripped of hospital identifiers and will be labeled with the study number and episode number before being shipped to the reference laboratory.

5.5.5 Efficacy Assessments

For the primary outcome, we will evaluate the plasma ammonia trajectory during episodes in which patients receive NCG vs. PLBO. Secondary outcomes will consist of FSS, and length of hospitalizations.

5.5.5.1 Functional Status Scale

The Functional Status Scale (FSS) will be used to assess changes in the subject's global functioning in the hospital setting. The measure will be obtained at baseline (i.e., prior to administration of study drug or placebo at each episode) and then daily during hospitalization up to discharge or for 7 days whichever is shorter. The scale includes 6 domains; mental status, sensory functioning, communication, motor functioning, feeding, and respiratory status. Each domain is rated on a 5-point scale from 1 (normal) to 5 (severe dysfunction), thus the range of overall scores is 6 to 30 (Table 4). The measure was designed to be quantitative, rapid, reliable, minimally dependent on subjective assessments, applicable to as broad an age range as possible, and pertinent to hospitalized patients in as many inpatient environments as possible²². All individuals collecting data will be trained in the measure and can include medical professionals such as a nurse, genetic counselor, or physician investigator at the site.

Table 2. The Functional Status Scale (from Pollack et al., 2009)

| | Normal (Score = 1) | Mild Dysfunction (Score = 2) | Moderate Dysfunction (Score = 3) | Severe Dysfunction (Score = 4) | Very Severe Dysfunction (Score = 5) |
|---------------------|---|---|---|--|---|
| Mental status | Normal sleep/wake periods; appropriate responsiveness | Sleepy but arousable to noise/touch/movement and/or periods of social nonresponsiveness | Lethargic and/or irritable | Minimal arousal to stimuli (stupor) | Unresponsive, coma, and/or vegetative state |
| Sensory functioning | Intact hearing and vision and responsive to touch | Suspected hearing or vision loss | Not reactive to auditory stimuli or to visual stimuli | Not reactive to auditory stimuli and to visual stimuli | Abnormal responses to pain or touch |
| Communication | Appropriate noncrying vocalizations, interactive facial expressiveness, or gestures | Diminished vocalization, facial expression, and/or social responsiveness | Absence of attention-getting behavior | No demonstration of discomfort | Absence of communication |
| Motor functioning | Coordinated body movements, normal muscle control, and awareness of action and reason | 1 limb functionally impaired | ≥2 limbs functionally impaired | Poor head control | Diffuse spasticity, paralysis, or decerebrate/decorticate posturing |
| Feeding | All food taken by mouth with age-appropriate help | Nothing by mouth or need for age-inappropriate help with feeding | Oral and tube feedings | Parenteral nutrition with oral or tube feedings | All parenteral nutrition |
| Respiratory status | Room air and no artificial support or aids | Oxygen treatment and/or suctioning | Tracheostomy | Continuous positive airway pressure treatment for all or part of the day and/or mechanical ventilatory support for part of the day | Mechanical ventilatory support for all of the day and night |

